### 3.1.4.2 Definition of Dose Limiting Toxicity (DLT)

The DLT is defined using the Common Terminology Criteria for Adverse Events Version 4.0 (CTCAE v4.0) in the first 21 days of treatment. All toxicities will be considered related to BVD-523 if they cannot be definitively explained by underlying disease, intercurrent illness or concomitant medications.

- Any treatment emergent study drug related Grade 3 or Grade 4 non-hematologic toxicity unless clearly and incontrovertibly unrelated to BVD-523. Exceptions are Grade 3 or 4 nausea or vomiting that is controllable by anti-emetics or Grade 3 or 4 diarrhea controllable by optimal therapy such as loperamide. Grade 3 laboratory investigations other than serum creatinine, bilirubin, AST or ALT will not be considered a DLT unless they are associated with clinical manifestations.
- Study-drug related Grade 4 thrombocytopenia that was not present at study entry and that does not resolve within 7 days, unless clearly and incontrovertibly unrelated to BVD-523.
- Febrile neutropenia or Grade 4 neutropenia that was not present at study entry and that does not resolve within 7 days, unless clearly and incontrovertibly unrelated to BVD-523.
- Prolonged myelosuppression or pancytopenia with a hypocellular bone marrow and no marrow blasts lasting for 6 weeks or more that is not related to disease progression.

• Any study drug related toxicity that results in treatment delays of > 4 days, except when patient is experiencing rash in which case, patient may be off drug for up to 7 days while receiving treatment.

All subjects who are not evaluable for toxicity in Cycle 1 due to unrelated AEs will be replaced.

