# 7 DISCONTINUATION CRITERIA

## 7.1 EARLY DISCONTINUATION OF THE STUDY

It is agreed that for reasonable cause, either the Investigator or the Sponsor may terminate this study, provided a written notice is submitted at a reasonable time in advance of intended termination. If discontinuation is by the investigator, notice is to be submitted to BioMed Valley Discoveries, Inc. If discontinuation is by the Sponsor, notice will be provided to each investigator.

If a severe local reaction or drug-related SAE occurs at any time during the study, the Safety Monitoring Committee will review the case immediately.

The study will be immediately suspended and no additional BVD-523 doses will be administered pending review and discussion of all appropriate study data by the SMC if one or more patients at any dose level develop any of the following adverse events deemed to be possibly, probably or definitely related to BVD-523 by the Investigator and/or Medical Monitor, based upon close temporal relationship or other factors:

- Death
- Anaphylaxis (angioedema, hypotension, shock, bronchospasm, hypoxia, or respiratory distress)

The study will not be restarted until all parties have agreed to the course of action to be taken and the Institutional Review Board/Ethic Committee (IRB/EC) (s) has/have been notified.

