# 8 TREATMENT

The safety and PK of BVD-523 will be tested in sequentially increasing doses starting at 300 mg twice daily, initially in patient cohorts of 3 patients (for tabular summary, see Table 3.2). Dose escalations of BVD-523 will occur in 100% increments in cohorts until one patient experiences a study related  $\geq$  Grade 2 toxicity (excluding alopecia or diarrhea), after which dose increases will be  $\leq$  50%. If one patient in a 3 patient cohort experiences a DLT as defined in Table 3.2, up to 3 additional patients will be treated at this dose level. If more than one DLT occurs in  $\leq$  6 patients, this dose level will be defined as the non-tolerated dose and dose escalation will be stopped.

Doses will not be escalated unless the patient(s) receiving the highest current dose have been observed for at least 3 weeks and dose-limiting side effects have been reported in less than 2 of 6 patients assigned to a given dose. Before each escalation, Clinical Investigators will be consulted to ensure that all involved agree with the escalation decision. Once the RP2D has been identified, up to 40 additional patients with pre-defined genetic types will be treated at this dose in Part 2.

Patients experiencing DLT or unacceptable toxicity will have their treatment interrupted until the toxicity returns to  $\leq$  Grade 1 or pre-treatment baseline (whichever is more severe). Resumption of BVD-523 treatment may then be at the next lower dose level where the safety profile has previously been established or between the dose level yielding unacceptable toxicity and the previous dose level, aligning with capsule dose availability.

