## 9.2 DEFINITION OF A SERIOUS ADVERSE EVENT

A Serious Adverse Event (SAE) is any untoward medical occurrence that occurs at any dose (including after the ICF is signed and prior to dosing) that:

- Results in death
- Is life-threatening (patient is at immediate risk of death from the event as it occurred)
- Requires in-patient hospitalization (formal admission to a hospital for medical reasons) or prolongation of existing hospitalization
- Results in persistent or significant disability/incapacity
- Results in a congenital anomaly/birth defect

Important medical events that may not result in death, are not life-threatening, or do not require hospitalization may be considered SAEs when, based on appropriate medical judgment, they may jeopardize the patient and may require medical or surgical intervention to prevent one of the outcomes listed in this definition. Examples of such events include allergic bronchospasm requiring intensive treatment in an emergency room or at home, blood dyscrasias or convulsions that do not result in in-patient hospitalization, or the development of drug dependency or drug abuse.

Hospitalizations for elective surgery or other medical procedures that are not related to a treatment-emergent AE are not considered SAEs.

Progression of the malignancy under study (including signs and symptoms of progression) should not be reported as an SAE unless the outcome is fatal during the study or within the safety reporting period (see below). If the malignancy has a fatal outcome during the study or

within the safety reporting period, then the event should be reported using the term "disease progression" with a CTCAE severity of Grade 5.

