#### **DLTs**

For this study, Dose Limiting Toxicities (DLTs) are based upon the first Cycle (first 21 days of treatment), defined as (where Grade refers to CTCAE v 4.0 categorization):

- Any treatment-emergent study drug related Grade 3 or Grade 4 non-hematologic toxicity unless clearly and incontrovertibly unrelated to BVD-523. Exceptions are Grade 3 or 4 nausea or vomiting that is controllable by anti-emetics or Grade 3 or 4 diarrhea controllable by optimal therapy such as loperamide. Grade 3 laboratory investigations other than serum creatinine, bilirubin, AST or ALT will not be considered a DLT unless they are associated with clinical manifestations.
- Study-drug related Grade 4 thrombocytopenia that was not present at study entry and that does not resolve within 7 days, unless clearly and incontrovertibly unrelated to BVD-523.
- Febrile neutropenia or Grade 4 neutropenia that was not present at study entry and that does not resolve within 7 days, unless clearly and incontrovertibly unrelated to BVD-523.
- Prolonged myelosuppression or pancytopenia with a hypocellular bone marrow and no marrow blasts lasting for 6 weeks that is not related to disease progression.
- Any study drug related toxicity that results in treatment delays of > 4 days, except when subject is experiencing rash in which case, subject may be off drug for up to 7 days while receiving treatment.

All subjects who are not evaluable for toxicity in Cycle 1 due to unrelated AEs will be replaced.

Dose escalation will proceed according to the following rules:

Observed Safety Outcomes	Action
1 DLT in 3 subjects	Expand cohort up to 6 subjects
1 DLT in 6 subjects	Escalate by $\leq 50\%$ to next dose level
> 1 DLT in ≤ 6 subjects	Stop dose escalation

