### 10.2 ADVERSE EVENTS

An adverse event is defined as any untoward medical occurrence in a subject administered a medicinal product that does not necessarily have a causal relationship with this treatment. This includes an exacerbation of pre-existing conditions or events, inter-current illnesses, drug interaction, or the significant worsening of the indication under investigation that is not recorded elsewhere in the eCRF under specific efficacy assessments. The reporting period of an AE begins from the time that the subject provides informed consent through and including 30 calendar days after the last administration of BVD-523 (or at the time when a subject begins a new anticancer therapy). Anticipated fluctuations of pre-existing conditions, including the disease under study that does not represent a clinically significant exacerbation or worsening, need not be considered AEs.

The severity of an AE will be graded according to the National Cancer Institute (NCI) Common Terminology Criteria for Adverse Events (CTCAE), version 4.03 with values of Grade 1 to Grade 5 (increased in severity). For AEs not covered by NCI CTCAE, the severity will be characterized as "mild," "moderate," or "severe" according to the following definitions:

- Mild events are usually transient and do not interfere with the subject's daily activities.
- Moderate events introduce a low level of inconvenience or concern to the subject and may interfere with daily activities.
- Severe events interrupt the subject's usual daily activities.

All AE relationship to the study drug, BVD-523, are classified as "unrelated," "possibly related," or "related."

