## **AE Summaries**

A subject who reported multiple AEs that map to a common PT or SOC is counted only once for that PT or SOC at the highest severity reported and at the greatest relationship to study drug. The number and percentage of subjects who experienced at least one AE as well as subjects who experienced at least one TEAE will be tabulated by SOC and PT with respect to dose level treatment group for each study part. The same tabulation will also be applied to any treatment emergent SAEs and any TEAEs leading to premature discontinuation from the study as well as to any DLTs.

Page 28

<sup>1 All toxicities will be considered related to BVD-523 if they cannot be definitively explained by underlying disease, intercurrent illness or concomitant medications.

The number and percentage of subjects who experience at least one TEAE will also be tabulated by SOC and PT within each dose level treatment group with respect to relationship to study drug (unrelated and at least possibly related [combining events classified as either possibly related or related]) and severity (Grade 1 to Grade 5 and ≥Grade 3). The tabulation by relationship

(unrelated and at least possibly related) will also be applied to any treatment emergent SAEs (TESAEs).

Subject listings will also be provided for all AEs, all SAEs, all AEs leading to early discontinuation from the study, all AEs leading to study drug interruptions and length of interruptions.

Bar graphs of AEs in CTCAE Term will be displayed in decreasing order of incidence from most common to least common. Each bar in the plot will represent an AE in CTCAE Term. Severity of AE (grades) will be embedded in each bar using the percentages of subjects in each AE grade. These plots will be provided for all AEs, TEAEs, treatment-emergent SAEs, and AEs leading to premature discontinuation from the study.

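### The non-hematologic DLT criterion stops at Grade 4, so a related event that is fatal from onset is not a DLT as written and can drop out of the rules and tables that use the DLT count

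*Protocol*

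**What the plan says.** Protocol 3.1.4.2 lists five DLT criteria, applied to the first 21 days of treatment. The non-hematologic one reads "Any treatment emergent study drug related Grade 3 or Grade 4 non-hematologic toxicity unless clearly and incontrovertibly unrelated to BVD-523", with exceptions for controllable nausea, vomiting and diarrhea and for most Grade 3 laboratory findings. SAP 3.1 has "Any treatment-emergent study drug related Grade 3 or Grade 4 non-hematologic toxicity unless clearly and incontrovertibly unrelated to BVD-523", and SAP 10.2 repeats it. The fifth criterion has no grade limit: "Any study drug related toxicity that results in treatment delays of > 4 days", with a longer allowance for rash. None of the five mentions death or Grade 5.

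Grade 5 is in use elsewhere. Protocol 9.2 has fatal progression reported "with a CTCAE severity of Grade 5". SAP 10.2 grades adverse events from 1 to 5, and its AE Summaries paragraph tabulates Grade 3 and above as one category.

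Protocol 7.1 suspends the study and all dosing after one death judged at least possibly related, pending review by the Safety Monitoring Committee (SMC). It adds: "The study will not be restarted until all parties have agreed to the course of action to be taken". It does not mention the DLT count.

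The count is used in four places:
- Part 1 escalation: Protocol Table 3.2, and Section 8, which requires that "dose-limiting side effects have been reported in less than 2 of 6 patients assigned to a given dose".
- The MTD definition: Protocol 3.1.4.1, below 33%.
- The Part 2 rule in Protocol 10.1.2: DLTs in more than 33% of a cohort with at least 6 enrolled, at any time, pause enrollment and require a lower dose for later patients.
- SAP tables 14.3.1.1-14.3.1.4.

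**The concern.** DLTs are a primary safety endpoint (SAP 2.3.1), and the definition followed literally omits the worst grade. Many fatal courses are still covered, because toxicity recorded at Grade 3 or 4 before death counts and so does febrile neutropenia. The gap is a related non-hematologic event that is Grade 5 at its first record.

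The consequence is a count that can be one too low. Part 1 escalation and the MTD use the same definition as Part 2, so the wording affects both. Part 1 is now largely past, since SAP 5.2 names 600 mg as the RP2D and SAP 15 says this version was revised for Part 2. Still open are whether the Part 2 rule fires, with its required dose reduction, and what the DLT tables report.

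**Working it through.** The plan computes no figure for this rule. Its one stated probability, 88% for at least one response in 20 patients at a true rate of 10%, concerns efficacy. It reproduces as 1 − 0.9^20 = 0.878 and plays no part below.

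**Step 1: does any criterion capture the event?**
- Non-hematologic criterion: Grade 5 is neither Grade 3 nor Grade 4, so no.
- Thrombocytopenia, neutropenia and prolonged myelosuppression criteria: these are hematologic, so no.
- Delay criterion: only if death is called a treatment delay of more than 4 days.
- Protocol 7.1: suspends and reviews, but adds nothing to the count.

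**Step 2: one snapshot.** Take 7 enrolled, one such death and two other DLTs.
- As written: 2/7 = 28.6%, below the limit.
- Death counted: 3/7 = 42.9%, above the limit.

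At n = 7 the rule needs 3 DLTs whether 33% is taken as 0.33 or as one third. The readings differ at n = 6, where 2/6 = 33.3% exceeds 0.33 but not one third. Under the literal reading the rule has therefore already fired at n = 6 if both other DLTs are among the first six patients. With all enrollment orders equally likely, the chance that the seventh patient is not one of those two is 5/7 = 71%. The snapshot shows the arithmetic of one omission. It does not give the chance of a changed decision.

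**Step 3: the rule over the whole of Part 2.** Inputs from Protocol 10.1.2 and 3.1.2 are a limit above 33%, at least 6 enrolled, applied at any time, and up to 20 per group. The following are assumed:
- exactly one such death in a group of 20, equally likely at each enrollment position;
- independent DLT risk p in the other 19 patients, with p = 10%, 20% or 30%;
- a look after every patient from n = 6, with outcomes known at once;
- enrollment otherwise running on to 20, ignoring the Protocol 7.1 suspension.

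Let k(n) be the other DLTs among the first n patients, and D(n) = 1 if the death is among them. As written, the rule fires at the first n ≥ 6 with k(n)/n > c. With the fix, it fires when (k(n) + D(n))/n > c. The probability comes from adding patients one at a time:

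P_n(k) = P_{n−1}(k)(1 − p) + P_{n−1}(k − 1)p

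At the death's position the count shifts by 0 (as written) or 1 (with the fix). Probability above the limit is removed and summed from n = 6, and the result is averaged over the 20 positions.

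| 33% read as | p | Ever fires, as written | Ever fires, death counted | Rise (points, approx.) |
|---|---|---|---|---|
| one third | 10% | 3.9% | 10.1% | 6 |
| one third | 20% | 24.0% | 39.8% | 16 |
| one third | 30% | 56.2% | 72.5% | 16 |
| 0.33 | 10% | 11.8% | 23.7% | 12 |
| 0.33 | 20% | 39.6% | 56.2% | 17 |
| 0.33 | 30% | 69.6% | 82.3% | 13 |

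All six rows are conditional on one such death having occurred.

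**The case against.** The strongest reply is that Protocol 7.1 already does more than the Part 2 rule. A single death judged even possibly related stops all dosing in both parts, whereas the Part 2 rule only pauses enrollment in one group. The SMC reviews every serious adverse event (Protocol 3.2), and deaths have their own tables, including by relationship (SAP 14.3.2). This stands, and it removes most of the safety consequence. It leaves two things open. After a restart, a lower dose is a matter for agreement under Section 7.1 but required under Section 10.1.2. The DLT tables would also still omit the event.

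A second reply is that the delay criterion has no grade limit and could take in a fatal event. Timing is no obstacle: the fourth criterion lasts 6 weeks, so the 21-day window cannot require every duration to finish inside it. The obstacle is the word delay, which does not naturally describe death. A sensible team might count the event anyway, and the SAP's use of Grade 3 and above elsewhere suggests a drafting slip. That is a reason to correct the text.

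A reader might infer that the plan would let the dose be raised after a drug-related death. The documents do not support that. Section 7.1 halts dosing, Section 8 limits dose-limiting side effects without stating a grade cap there, and investigators are consulted before each escalation. Nor do they show that such deaths are to be expected: none of the five DLT patients listed from the first study (Protocol 2.1) is described as having died.

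**Conclusion.** Wrong as written, and minor. The definition, in all three places, omits a related non-hematologic event that is Grade 5 from onset, and no other provision clearly puts it into the DLT count. It does not follow that such a death would go unseen or that dosing would simply continue.

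The size is one event in the count. Under the assumptions in the working, and given that one such death occurs in a group of 20, the chance that the Part 2 rule ever fires is lower as written by about 6, 16 and 16 points (one third) or 12, 17 and 13 points (literal 33%) at risks of 10%, 20% and 30%. Those risks, the immediate knowledge of outcomes and the disregard of the Section 7.1 suspension are assumptions. No overall probability can be given, because the documents contain no rate for such deaths. The wording gap itself rests on no assumption.

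**What to change.** In Protocol 3.1.4.2, SAP 3.1 and SAP 10.2, replace Grade 3 or Grade 4 in the opening words of the non-hematologic criterion with Grade 3 or higher. Keep the existing exceptions for controllable Grade 3 or 4 nausea, vomiting and diarrhea and for Grade 3 laboratory findings. Add a sentence that a related death in Days 1-21 counts as a DLT under the attribution rule already in Section 3.1.4.2, including for the Part 2 rule and tables 14.3.1.1-14.3.1.4.

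No new data are needed. The protocol change requires an amendment approved by the sponsor, the IRB/EC and the health authorities (Protocol 10.4). Section 3.1.4.2 presumes relatedness unless another cause definitively explains the event, so some early AML or MDS deaths of unclear cause would count and could pause a Part 2 group. The same presumption already applies to Grade 3 and 4 events. Part 2 would also run under slightly different wording from that in force when the RP2D was chosen, which the report should state.

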#### 3.1.4.3 Definition of Recommended Phase 2 Dose (RP2D)

The Recommended Phase 2 Dose (RP2D) may be as high as the MTD and will be determined in discussion with the Clinical Investigators, the Medical Monitor, and the Sponsor. Observations related to pharmacokinetics, pharmacodynamics, and any cumulative toxicity observed after multiple cycles may be included in the rationale supporting the RP2D.

## 3.2 SAFETY MONITORING COMMITTEE

An internal Safety Monitoring Committee (SMC) will be set up to review the safety of BVD-523 as the study progresses. The SMC will consist of Clinical Investigators, the Medical Monitor and Sponsor representatives. The SMC will review any serious Adverse Event (SAE) that occurs during the study and will examine the safety of each dose level of BVD-523, including toxicities that may occur in later cycles of treatment.

### 3.3 SAFETY REVIEW MEETINGS

The safety review will be performed in all stages of the dose escalation:

- Prior to starting each new dose level after the initial cohort.
- To stop the dose escalation if the MTD has been reached.
- An update on patient status will be provided to each investigator semi-monthly.

## 3.4 STOPPING RULES

The entire study or treatment of individual patients may be stopped under defined circumstances as outlined in Section 7: Discontinuation Criteria.

## 3.5 CRITERIA FOR EVALUATION

#### 3.5.1 Safety

- Vital signs
- Physical examination
- Ophthalmology examination
- Clinical chemistry
- Hematology
- Urinalysis
- ECGs
- Severity of AEs (graded according to the NCI CTCAE Grading System Version 4.03 as detailed on web page: http://ctep.cancer.gov).

### 3.5.2 Efficacy

• Clinical response will be assessed on results of bone marrow biopsies using International Working Group 2003 and 2006 criteria for AML or MDS, respectively (1, 2).

#### 3.5.3 Pharmacokinetics

- Blood samples will be collected to measure BVD-523 and selected metabolite concentration levels.
- At Baseline (Visit 2, Cycle 1) and again on Day 22 (Visit 5, Cycle 1), blood samples will be collected prior to administration of the first dose and then post-dosing at the following time points: 0.5, 1, 2, 4, 6, 8, and 12 ± 2 hours.

### 3.5.4 Pharmacodynamics

• Blood and/or bone marrow aspirate will be used to evaluate multiple biomarkers of drug response including pRSK and total RSK. Blood and/or bone marrow aspirate will be collected to measure *ex vivo* BVD-523 sensitivity of leukemic cells prior to therapy on Day 1 and Day 22. Additional biomarkers and DNA sequence analysis may be identified and measured as appropriate by collection of whole blood prior to dosing initiation and after drug levels have reached steady-state.

## 3.6 BLINDING AND RANDOMIZATION

This study is designed as an open-label study. All patients will receive treatment with orally administered BVD-523.

# 4 SELECTION OF PATIENTS

## 4.1 NUMBER OF PATIENTS

In this study, up to approximately 20 patients with AML or MDS, regardless of RAS mutation status, will be enrolled in Dose-escalation Part 1. Three to six patients per treatment cohort will be assigned to receive sequentially higher oral doses of BVD-523.

In the Cohort-expansion Part 2, additional patients with RAS mutant positive AML or MDS and RAS mutant negative AML or MDS will be recruited for treatment at the RP2D determined from Part 1 above.

Part 2 patients will receive twice daily oral doses of BVD-523 in 21-day treatment cycles until disease progression, unacceptable toxicity, or another withdrawal criterion is met. Treatment cycles will occur consecutively without interruption except when necessary to manage AEs.

Total enrollment for Part 2 is targeted for up to approximately 40 patients. Patients will be enrolled into 1 of 2 treatment groups. Group assignments are made according to the following disease characteristics:

- Group 1: Patients with RAS mutant positive AML or MDS; n (evaluable)  $\leq 20$
- Group 2: Patients with RAS mutant negative AML or MDS; n (evaluable)  $\leq 20$ .

